In our recently completed RELIEF trial, in which we enrolled near-identical patients to that proposed in this trial, the pooled incidence of SSI was 14% (consistent with global data²) and red cell transfusions were used in 12% of patients. An incidence of SSI of up to 25% has been reported in other at-risk major gastrointestinal surgical cohorts.43, 44 Assuming an incidence of 12%, and using a type I error of 0.05, we require 1,484 per group in order to have 90% power to detect a 30% reduction in SSI to 8.4% (i.e. relative risk 0.7). Were the control group incidence 14%, this sample size provides 94% power to detect a 30% reduction to 9.8%. We plan to enrol 3,300 patients. This will also provide ≥90% power to detect a 30% reduction in blood transfusions.

Assuming 30% of patients are diabetic and an incidence of SSI in non-diabetic patients in the placebo arm of 10%, this sample size provides \approx 70% power to detect a difference in treatment relative risks of 0.55 in non-diabetic patients and 0.94 in diabetic patients on the multiplicative relative risks scale.45

12. Framework

This trial uses a superiority hypothesis testing framework between groups for the primary outcomes. Results will be reported in accordance with the CONSORT 2025 statement.

13. Statistical interim analyses and stopping guidance

Interim analyses will consider the defined study and safety endpoints after enrolment of 50% and 75% of patients, adjusted according to the O'Brien and Fleming method. Results will be made available to the DSMC, consisting of experts in the fields of surgery, infectious diseases and anaesthesia, and an independent statistician (Chair: [name], UK).

Section 4: Statistical Principles

14. Level of statistical significance

All applicable statistical tests will be 2-sided and will be performed using a 5% significance level.

15. Description of any planned adjustment for multiplicity, and if so, including how the type 1 error is to be controlled

No adjustment for multiplicity is planned.

16. Confidence intervals to be reported

All confidence intervals will be two-sided 95% confidence intervals.

17. Analysis Populations and Estimand

Except where stated otherwise, all analyses will be conducted under the principle of modified intention-to-treat, whereby all participants are included in their randomised groups, but only those participants who underwent a surgical incision will be included in the analysis.

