These outcomes will be compared between groups using mixed effects linear regression models adjusting for the stratification variable of diabetes, with random effects for the stratifying variable of site.

25. Statistical Methods – adjustment for covariates

Supplementary analyses for the primary outcome and the secondary outcome of any red cell transfusion will adjust for any prognostic variables imbalanced at baseline.

For the primary outcome, variables with apparent imbalance out of the following list will be adjusted for:

- Patient age
- ASA physical status
- Diabetes
- Current smoker
- Oral steroid
- Open surgery

For the outcome of any red cell transfusion, variables with apparent imbalance out of the following list will be adjusted for:

- Patient age
- ASA physical status
- Body mass index (weight/height²)
- Chronic renal disease
- Aspirin
- Preoperative haemoglobin
- Open surgery

26. Statistical Methods – subgroup analyses

Subgroup analyses of the primary outcome and any red cell transfusion will be conducted for the following subgroups:

- i) Age strata (\leq 60 yr; 61–70 yr;71–75 yr;>75 yr);
- ii) Patient sex;
- iii) BMI strata (≤ 18.5 ; $\geq 18.5-25.0$; $\geq 25.0-30.0$; $\geq 30.0-35.0$; ≥ 35.0);
- iv) ASA physical status
- v) Diabetes status (i.e. the stratification variable);
- vi) Country;
- vii) Type of GI surgery;
- viii) Duration of surgery (approximate quartiles)

Models for these analyses will be as described in Section 27 for the primary analysis, including terms for the subgroup indicator and interactions between the subgroup and randomised group. Treatment effects in each subgroup will be reported.

27. Missing data reporting and assumptions/statistical methods to handle missing data

Multiple imputation of outcomes will be undertaken if the proportion of missingness of the primary outcome

is >5%.

Missing baseline characteristics will be imputed using single mean imputation. Baseline characteristics of participants who did and did not provide the primary outcome will be compared, and will be used to inform multiple imputation models. T-tests or Wilcoxon rank-sum tests will be used to compare continuous characteristics (depending on whether these had approximately symmetric distributions or not); chi-squared tests will compare categorical characteristics between participants with and without the primary outcome.

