Missing outcome values will be imputed separately by treatment group. Imputation models will include treatment group, diabetes status, and baseline characteristics that appear to be different between participants who provided complete follow up data and participants who did not. Imputation models for continuous outcomes will also include terms for site. Imputation models for binary outcomes will not include terms for site due to the possibility of perfect prediction in small sites.

Initially, imputation via chained equations will be attempted for outcomes, with separate imputation for each outcome if this imputation fails. Binary outcomes will be imputed using logistic regression models, and continuous outcomes imputed via with predictive mean matching from the 5 nearest neighbours. Imputed datasets will be compared to complete data using density plots for continuous outcomes and plots of proportions for binary outcomes.

28. Additional Analyses

As-treated and per protocol analyses of the primary outcome and any red cell transfusion will also be conducted. As noted in the E9(R1) addendum, these additional analyses may be subject to severe bias and may not correspond to a relevant estimand.

Data collected prior to the trial re-start (the "contamination dataset") will also be considered. A table summarizing the baseline characteristics of patients by randomised treatment group will be presented. The primary outcome, red cell transfusion outcomes, and healthcare associated infections will be analysed as described above in this dataset.

29. Harms

Safety outcomes and adverse events will be reported by treatment group.

30. Statistical Software and code

Stata v19 or later will be used (StataCorp. Stata Statistical Software: Release 19. College Station, TX: StataCorp LLC); or R v 4.4.1 or later. Any user-written R packages used will be referenced.

The following code will be applied for the analysis of primary and secondary outcomes:

Primary outcome and binary secondary outcomes:

```
xi: gllamm outcome i.TreatmentGroup i.diabetes, i(site) fam(binomial)
link(log)
```

Primary outcome and binary secondary outcome backup code:

```
binreg outcome i.TreatmentGroup i.diabetes, rr cluster(site)
```

DAH30:

```
qreg2 outcome i.TreatmentGroup i.diabetes, cluster(site)
qreg2 outcome i.TreatmentGroup i.diabetes, cluster(site)
```

Continuous outcomes:

mixed outcome i.TreatmentGroup i.diabetes || site: , reml

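### Imputation predictors are chosen only by association with missingness, so subgroup factors other than diabetes can be left out and their imputed-data subgroup effects pulled toward the overall RR

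*SAP*

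**What the plan says.** Sections 17 and 27 of the SAP call for multiple imputation when more than 5% of primary outcomes are missing. Section 27 imputes each arm separately. The predictors are treatment group, diabetes status and "baseline characteristics that appear to be different between participants who provided complete follow up data and participants who did not". Site is kept out of the models for binary outcomes. Chained equations are tried first, with outcome-by-outcome imputation as the fallback. Section 22 describes the comparison by follow-up status as a way to find auxiliary variables.

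Section 26 analyses SSI and any red cell transfusion by age, sex, BMI, ASA status, diabetes, country, type of surgery and duration of surgery, with models "including terms for the subgroup indicator and interactions between the subgroup and randomised group". It refers to Section 27 for those models, but Section 27 is the missing-data section and the models are in Section 24. The SAP therefore does not settle whether the subgroup analyses use imputed data. Section 17 promises a complete-case result for the primary analysis; nothing comparable is promised for the subgroups.

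Section 25 plans supplementary adjusted analyses in which "variables with apparent imbalance out of the following list will be adjusted for".

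**The concern.** An imputation model should contain the variables and interactions of the analysis that will use the imputed data. Section 27 instead selects on association with missingness. A subgroup factor unrelated to missingness is exactly the one that the rule leaves out.

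Once a factor is left out, imputed outcomes within an arm do not depend on it directly. The imputed patients then dilute any real difference between its levels, and the subgroup RRs drift toward the overall RR. This happens even when data are missing completely at random, where a complete-case subgroup analysis would be unbiased.

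Of the eight subgroup factors, only diabetes is guaranteed a place. Country cannot be represented through site, because site is barred from the binary models. Duration of surgery is not a baseline characteristic, so the wording gives it no route in, even if it differs by follow-up status.

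At stake are subgroup effects that will be reported for two outcomes. The error always favours apparent homogeneity, in comparisons with limited power to begin with.

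**Working it through.** **Reproducing the plan's figures.** Section 11 starts from "Assuming an incidence of 12%, and using a type I error of 0.05". Its result is 1,484 patients in each arm, for 90% power against a TxA risk of 8.4% (RR 0.7). Section 14 sets a two-sided 5% level. With the pooled-variance formula:

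n = [1.960 × √(2 × 0.102 × 0.898) + 1.2816 × √(0.12 × 0.88 + 0.084 × 0.916)]² / 0.036² = 1,484 per group, which agrees with the plan. Power at 14% versus 9.8% is 94.3%, against 94% stated.

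**Inputs for the illustration.**
- Section 11: "We plan to enrol 3,300 patients", taken here as 1,650 per arm.
- Section 11: "Assuming 30% of patients are diabetic and an incidence of SSI in non-diabetic patients in the placebo arm of 10"%, with RRs of 0.55 (non-diabetic) and 0.94 (diabetic).
- Derived: placebo risk in the smaller stratum = (0.12 − 0.7 × 0.10)/0.3 = 16.7%, taking 12% as the overall placebo risk.
- Assumed: the missing fraction m. The SAP gives only the 5% trigger, so 5.1% to 20% is shown.
- Assumed: a factor that is not diabetes has this same contrast. The SAP posits no contrast for any affected factor; the diabetes figures are borrowed for scale only.

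With these inputs the variance of the interaction log RR is 0.9/115.5 + 0.945/63.5 + 0.833/82.5 + 0.843/77.6 = 0.0436, so SE = 0.209. A Wald test then has 72.8% power at 1,650 per arm (68.2% at 1,484), in line with the stated figure of about 70%.

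**Attenuation when the factor is omitted.** With arm-specific imputation and missingness unrelated to the factor, the expected risk in a subgroup after imputation is

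(1 − m) × p(subgroup, arm) + m × p(arm).

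The arm averages are 0.12 (placebo) and 0.7 × 0.055 + 0.3 × 0.1567 = 0.0855 (TxA), so the overall RR is 0.7125. At m = 10%:

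- Larger stratum: (0.9 × 0.055 + 0.1 × 0.0855)/(0.9 × 0.10 + 0.1 × 0.12) = 0.05805/0.102 = 0.569.
- Smaller stratum: (0.9 × 0.1567 + 0.1 × 0.0855)/(0.9 × 0.1667 + 0.1 × 0.12) = 0.14955/0.162 = 0.923.

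| Assumed m | RRs after imputation | Ratio of RRs | Shrinkage of log ratio |
|---|---|---|---|
| 0 | 0.550 / 0.940 | 1.71 | 0 |
| 5.1% | 0.560 / 0.932 | 1.66 | 5.0% |
| 6% | 0.562 / 0.930 | 1.66 | 5.9% |
| 10% | 0.569 / 0.923 | 1.62 | 9.8% |
| 15% | 0.578 / 0.914 | 1.58 | 14.6% |
| 20% | 0.588 / 0.905 | 1.54 | 19.3% |

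The overall RR is 0.7125 in every row. With the factor in the arm-specific model, the expected values return to 0.55 and 0.94.

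**Size against sampling error.** At 10% missing the log ratio falls from 0.536 to 0.484, and 0.052/0.209 = 0.25 SE. At 6% it is 0.032/0.209 = 0.15 SE.

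**Simulation.** A run of 400 trials at 20% missing gave a ratio of RRs of 1.55 with the factor omitted and 1.68 with it included (true value 1.71). This supports the direction. The Monte Carlo error, at least 0.209/√400 = 0.010 on the log scale, is too large to confirm the small shifts near the trigger, so the sizes above rest on the formula.

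**Section 25 covariates.** Assume a true RR of 0.70, a covariate with RR 2 and prevalence 30% (placebo) versus 35% (TxA), and 10% missing. The unadjusted RR is 0.70 × 1.35/1.30 = 0.727. If the covariate is omitted from imputation, the stratum RRs are (0.9 × 0.70 + 0.1 × 0.945)/(0.9 + 0.1 × 1.30) = 0.703 and (0.9 × 1.40 + 0.1 × 0.945)/(0.9 × 2 + 0.1 × 1.30) = 0.702. The error is at most about 0.4%.

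**The case against.** The strongest reply is that the effect is conditional and small. Nothing happens unless more than 5% of primary outcomes are missing and the subgroup analyses use imputed data. SSI is ascertained by daily in-hospital review and a 30-day record review. Transfusion is counted only to discharge, so its attenuation follows its own missing fraction, and the SSI figures cannot be carried over to it. All of this stands.

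The illustration also borrows the one contrast that is protected. With a milder assumed contrast (0.65 versus 0.80, equal strata and equal baseline risks), 10% missing gives 0.658 and 0.793. That stands too: the 0.55 and 0.94 figures show scale and do not predict any factor's effect.

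A reader might infer that every imputed patient simply receives the arm-average risk. The SAP does not support that. Diabetes is always in the model, and the chained equations may let sepsis, anastomotic leak, CRP or transfusion carry part of the relation between a factor and SSI. The formula is therefore close to an upper bound. The fallback to separate imputation would remove that help.

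A reader might also infer that the covariate-adjusted analyses are biased by about the missing fraction. They are not. Section 25 estimates a single adjusted RR with no interaction to dilute, and omission leaves only a small part of a chance imbalance uncorrected.

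None of this defends the rule itself. It still drops analysis-model factors because they are unrelated to missingness.

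**Conclusion.** The concern holds for the Section 26 subgroup factors other than diabetes. Six of them can be left out of the imputation models, and duration of surgery cannot enter. If imputation is triggered and its data feed the subgroup analyses, the affected subgroup RRs and interactions are pulled toward the overall RR by up to about the missing fraction of the outcome concerned, even when data are missing completely at random. Under the assumed contrast and an assumed 10% missing this is about 0.57 and 0.92 instead of 0.55 and 0.94, or 0.25 SE.

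It would be wrong to read this as a threat to the main result. The primary RR does not move in this calculation. The diabetes interaction, the only one with a power statement, is preserved because diabetes is always a predictor and the arms are imputed separately. This is a modest, avoidable bias in secondary analyses. It is worth correcting because the rule as written builds it in and the remedy is cheap.

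**What to change.** In Section 27, require all Section 26 subgroup factors, including duration of surgery, in the arm-specific imputation models for SSI and any transfusion, in the form used in the analysis. Pool sparse levels such as small countries, which also limits perfect prediction. Keep imputation separate by arm, since this preserves the treatment interaction for every factor included. Use the follow-up comparison only to add auxiliary variables, as Section 22 implies.

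In Section 26, change the cross-reference from Section 27 to Section 24 and state whether the subgroup analyses use imputed data.

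The cost is SAP wording and a larger imputation model. At 1,650 per arm and risks of 8.4% to 12%, about 140 to 200 SSI events per arm are expected before missingness, which gives reasonable support. Some attenuation will remain among levels that are pooled.

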The primary estimand of interest is described in the table below.

Objective: To determine whether TxA, compared to matched placebo, decreases the risk of surgical site infection.

Estimand: Relative risk of incidence of any surgical site infection (superficial, deep, or organ space) among adult patients undergoing elective or semi-elective open or lap-assisted gastrointestinal surgery (oesophageal, gastric, hepatobiliary, pancreatic, colorectal) with one or more risk factors for complications assigned to receive treatment, relative to assignment to receive a matched placebo.

Treatment: 0.15 ml/kg TxA 15mg/kg before surgical incision, and then infusion at 0.05 ml/kg/h until end of surgery

surgery			
ESTIMAND	ANALYSIS		
Target population : adult patients undergoing elective or semi-elective open or lap-assisted gastrointestinal surgery (oesophageal, gastric, hepatobiliary, pancreatic, colorectal) with one or more risk factors	Analysis set: All randomized participants who undergo surgery. Patients assigned to receive TxA through randomization will be the treatment group, patients assigned to receive the placebo the comparator group.		
Variable: SSI (superficial, deep, and organ space), as defined by the US Centers for Disease Control (CDC), 14 up to 30 days after surgery. This includes all five separate categories of SSI, (Superficial Incisional Primary, Superficial Incisional Secondary, Deep Incisional Primary, Deep Incisional Secondary and Organ Space infection).	Outcome measure: Surgical site infection. Trial patients will be seen and have their medical records (and any cultures done) reviewed on a daily basis whilst in hospital, and a formal wound inspection done on Day 3 and day of discharge, plus a 30-day medical record/pathology review done. Any late (>30 postoperative days) notifications of SSI up to 90 days after surgery will be included in the outcome.		
Handling of intercurrent events: - Treatment as randomized not received:	Handling of missing data : Multiple imputation will be applied if >5% of the participants in the analysis		

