patients included in their randomized groups (treatment policy strategy) - Death prior to identification of SSI within the relevant window: if a patient dies prior to the identification of an SSI, their outcome will be "no SSI" ("while alive" strategy)	set have a missing primary outcome. Results of a complete case analysis will also be provided. Supplementary analysis: The analysis of the primary outcome will be repeated in As-treated and Per Protocol analysis sets.		

The relative risk

will

Population-level summary measure: Relative risk | Analysis approach:

of SSI if treated with TxA compared with no TxA.	estimated using a log-binomial model adjusted for the
	stratification variable of diabetes, with random effects
	for the stratifying variable of site.

Section 5: Trial Population

18. Screening Data

Screening data will be collected and a CONSORT flow diagram will be used to summarise this data.

19. Eligibility

Trial inclusion criteria are described in the trial protocol. Reasons for exclusion will be summarised in the CONSORT flow diagram.

20. Recruitment

A CONSORT flow diagram will be used to describe the number of people consented to participate, randomised, allocated to each treatment group, those lost to follow up (including reasons) and analysed.

21. Withdrawal/follow-up

All participants who are enrolled and randomly assigned to a group, and undergo surgery, must be followed for the duration of the study (unless they withdraw consent) even if they are withdrawn from the active phase of the trial. Losses to follow-up (including reasons) will be summarised in the CONSORT flow diagram by treatment group.

22. Baseline descriptive measures

Baseline characteristics will be summarised as appropriate (means and standard deviations for continuous variables that appear to be distributed approximately symmetrically, medians and interquartile ranges for other continuous variables, counts and percentages for categorical variables). Tests of statistical significance will not be undertaken for comparing baseline characteristics of treatment groups; rather the clinical importance of any imbalance will be noted.

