Blood transfusion reactions	Binary outcome: any incidence of transfusion reaction	Binary variable 0 = no transfusion reaction; 1 = transfusion reaction	Any blood transfusion reaction following any blood product transfusion

24. Analysis methods

Analysis of primary outcome, and binary secondary/safety outcomes:

For the primary analysis of binary outcomes, we will use log-binomial models adjusting for the stratification variable of diabetes, with random effects for the stratifying variable of site. If that model fails to converge, a log-binomial model with the same link function and adjusting for the stratification variable of diabetes but with cluster-robust standard errors instead of random effects for site. Results will be expressed as risk ratios with 95% confidence intervals.

For analyses based on multiply imputed datasets: if a model fails to converge for more than one quarter of imputed datasets, the model with cluster-robust standard errors will instead be fit.

Days at home up to 30 days after surgery

DAH30 will be compared between groups using median regression adjusting for the stratification variable of diabetes, with cluster robust standard errors for site. DAH-30 is calculated using mortality and hospitalisation data from the date of the index surgery (= Day 0). For example, if a patient died on day 2 after their surgery whilst still an inpatient, they would be assigned zero (0) days at home; if a patient was discharged from hospital on Day 6 after surgery but was subsequently re-admitted for 4 days before their second hospital discharge, then they would be assigned a DAH-30 value of 20. If a patient has complications and spends 16 days in hospital, and then is transferred to a nursing facility for rehabilitation, and spend 24 days there before finally being discharged to their own home, they would be assigned a DAH-30 value of zero (0), even though 30-16-

24 = -10 because the minimum value of DAH-30 should be zero. If a patient dies within 30 days of surgery, irrespective of whether they have spent some time at home, DAH-30 will be scored as zero (0).

In addition to presenting a difference in medians between groups with respect to DAH-30, a difference in lower quartiles (i.e. 25th percentiles) will be presented.

Peak C Reactive protein and volume of red blood cell transfusion

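### Safety outcomes are compared only by assigned arm; a supplementary table by study drug actually received would cheaply guard against possible dilution of harm

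*SAP*

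**What the plan says.** Section 17 sets the default: "Except where stated otherwise, all analyses will be conducted under the principle of modified intention-to-treat". It explains that under this principle "all participants are included in their randomised groups, but only those participants who underwent a surgical incision will be included in the analysis". The estimand table in the same section fixes what the groups mean for the primary outcome: "Patients assigned to receive TxA through randomization will be the treatment group". The table also lists failure to receive the randomised treatment as an intercurrent event, handled by treatment policy, so these patients stay in their assigned arm.

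Section 24 puts safety under the primary outcome's model through its subheading "Analysis of primary outcome, and binary secondary/safety outcomes". Section 29 says only that "Safety outcomes and adverse events will be reported by treatment group". Neither section makes an exception to the Section 17 default.

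Section 28 then adds analyses by treatment received: "As-treated and per protocol analyses of the primary outcome and any red cell transfusion will also be conducted". It cautions that these can be severely biased and may not match a relevant estimand. Safety outcomes are not on that list. They are also not among the outcomes to be analysed in the data collected before the trial restart.

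**The concern.** The SAP expects that some patients will not get what they were randomised to, and it plans an as-treated analysis because of this. It uses that analysis for two efficacy outcomes only. In a superiority trial, dilution of a benefit toward no difference is the cautious error. Dilution of a harm is the incautious one. The outcomes where a grouping by exposure could add most to interpretation are the ones without it.

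Under assigned-arm grouping, a TxA-assigned patient who received no study drug is counted as exposed while carrying only background risk. A placebo-assigned patient who was given TxA and then had an event is counted as a placebo event. If either happens often enough, a report of little or no excess harm could partly reflect misclassified exposure, and the SAP plans no companion table by which a reader could judge this. Adding one after the harm results are known would look post hoc.

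**Working it through.** **What the text fixes.** Section 17 makes the randomised group the default for every analysis unless an exception is stated. Sections 24 and 29 state none for safety. Section 28 states one for SSI and any red cell transfusion. Section 29 does not spell out what it means by treatment group, but with Sections 17 and 24 and the estimand table, the assigned arm is the only reading that the SAP supports.

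**The plan's own figure.** The SAP gives no figure on this point. Its sample size (Section 11) was reproduced to check the power formula used below. For 12% versus 8.4%, two-sided 0.05 and 90% power, with pooled variance and no continuity correction, the mean risk is 0.102 and

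n = [1.960·√(2·0.102·0.898) + 1.282·√(0.12·0.88 + 0.084·0.916)]² / 0.036² = 1,484 per group,

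as stated. This does not bear on the safety question itself.

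**Dilution: inputs.** All are assumed, because the SAP gives no safety event rates, harm effect, non-receipt rate or crossover rate:
- p0 = 1%, the risk without TxA
- p1 = 2%, the risk with TxA (true risk ratio 2.0)
- a = share of the TxA arm not given TxA
- b = share of the placebo arm given TxA
- non-receipt and crossover unrelated to the patient's risk

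**Formula.** By-assignment RR = [(1−a)·p1 + a·p0] / [(1−b)·p0 + b·p1].

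| Case | a | b | TxA arm | Placebo arm | RR |
|---|---|---|---|---|---|
| Full receipt | 0 | 0 | 2.00% | 1.00% | 2.00 |
| Non-receipt, TxA arm only | 2% | 0 | 1.98% | 1.00% | 1.98 |
| Non-receipt, TxA arm only | 5% | 0 | 1.95% | 1.00% | 1.95 |
| Non-receipt, TxA arm only | 10% | 0 | 1.90% | 1.00% | 1.90 |
| TxA given in placebo arm only | 0 | 5% | 2.00% | 1.05% | 1.90 |
| TxA given in placebo arm only | 0 | 10% | 2.00% | 1.10% | 1.82 |
| Crossover in both arms | 2% | 2% | 1.98% | 1.02% | 1.94 |
| Crossover in both arms | 5% | 5% | 1.95% | 1.05% | 1.86 |
| Crossover in both arms | 10% | 10% | 1.90% | 1.10% | 1.73 |

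With a true risk ratio of 1.5, the by-assignment value is 1.49 (a = 2%, b = 0), 1.475 (a = 5%, b = 0), 1.44 (5% both ways) and 1.38 (10% both ways).

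**Power.** This uses the same two-proportion formula with 1,650 per arm (half of the planned 3,300) and a true risk ratio of 2.0.
- Background risk 1%: 66% with full receipt, 62% at a = 5% and b = 0, 57% at 5% both ways, 47% at 10% both ways.
- Background risk 2%: 92%, 90%, 86% and 77% for the same cases.

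**Anaphylactoid reactions.** Section 23 defines these as following study drug administration. A patient who received no study drug cannot have the event as defined but stays in the denominator. If shares a and d of the TxA and placebo arms received no study drug, the ratio becomes (1−a)·p1 / [(1−d)·p0]. When a = d the factors cancel, so the risk ratio is distorted only if non-receipt differs between arms.

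**The case against.** The strongest reply is that nothing here is wrong. Sections 17, 24 and 29 agree with each other, and the comparison they fix is the randomised one, free of confounding. The SAP itself warns that as-treated analyses may be severely biased. If patients given open-label TxA are sicker or bleeding, moving them into the TxA group could create apparent harm. Withholding the drug from patients thought to be at thrombotic risk would bias the other way. A gap between the two tables could then be dilution or confounding, and the table cannot say which.

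The size may also be small. This is a double-blind trial of a single perioperative bolus and infusion against matched placebo. The SAP names non-receipt, not crossover, and never mentions open-label TxA. With non-receipt in the TxA arm alone, the loss is 2.00 to 1.95 at 5%. Safety-set conventions may also stand in the protocol, which was not available for this point.

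Much of this stands. It sets the limits of the point:
- A reader might infer that the by-assignment safety analysis is invalid. It is not.
- A reader might infer that TxA harm will be diluted. The documents do not support that: there is no dilution if everyone receives the assigned drug, no rate is given, and the direction is assured only if non-receipt is unrelated to risk.
- A reader might infer that one misclassified anaphylactoid case would erase a difference. No event rate in the SAP allows that to be calculated.

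What does not stand is the bias warning as a reason to leave harm out. The SAP accepted the same caveat for two efficacy outcomes. Low non-receipt is no reason either, since the two tables would then agree and reassure the reader.

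**Conclusion.** The point holds as a cheap improvement. The SAP compares safety outcomes only by assigned arm and reserves its as-treated analysis for SSI and any red cell transfusion. The assigned-arm comparison should remain primary. It may understate a relative harm if study drug is not received as assigned.

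On the assumed figures the understatement is slight for the event that the SAP names, non-receipt in the TxA arm. It becomes material only with crossover of 5–10% in both arms, which nothing in the SAP suggests. These sizes rest on an assumed 1% background risk, a true risk ratio of 2.0, and non-receipt or crossover unrelated to risk. The power figures for 2% background risk show that the loss of power also depends on the event rate.

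**What to change.** Add one sentence to Section 28 and refer to it in Section 29. Thromboembolism, seizures, cardiovascular events and anaphylactoid reactions will also be tabulated among patients who received any study drug, grouped by the study drug actually received, as a supplement shown beside the by-assignment table. The sentence should define receipt, because the SAP does not define its As-treated set.

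Grouping by any TxA received, open-label included, should be no more than a further sensitivity analysis, since that is where confounding is most likely. The main supplementary table will therefore not correct for open-label TxA in the placebo arm (1.90 and 1.82 in the working). Keep the existing Section 28 caveat and extend it to these outcomes.

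The cost is one sentence and one table, from receipt data that the planned as-treated analysis already needs. The downside is possible confounding if non-receipt is related to risk, which is why the table stands beside the randomised comparison and does not replace it.
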